8.1.2. Planned Safety Statistical Analyses

Planned Statistical Analyses
Endpoint(s)
• Oxygen Saturation
Model Specification

 • Refer to Section 7.2. Oxygen Saturation will be analysed in the same manner as for the primary endpoint PASP. • Posterior probabilities of interest include (looking for very low probabilities to remove any concerns with regards to Oxygen Saturation reduction on GSK2586881): 
 • Probability that the change from baseline on Oxygen Saturation is reduced by GSK (i.e., probability that a treatment difference is <0% or if a log transformation is applied then the probability that the ratio < 1).

Planned Statistical Analyses

 Probability that the change from baseline in Oxygen Saturation is reduced by GSK by >3% and >=5% (absolute difference) compared to placebo. (i.e., probability that a treatment difference (absolute) is <-3% and <=-5%. In the case of a log-transformation, ratios of interest would be <0.94 and <0.92 representing 6% and 8% difference between groups) Probability cut-offs may be re-assessed at the time of analysis
Model Checking

 Refer to Appendix 8: Model Checking and Diagnostics for Statistical Analyses.
Model Results Presentation

 Summary tables for absolute and change from baseline by treatment and timepoint (T0 to T4) (for Part 1 and Part 2) Listing of absolute data Individual subject profiles by treatment group and timepoint (for Part 1 and Part 2) Summary table of statistical analysis, adjusted change from baseline posterior medians and 95% credible intervals by treatment and timepoint, together with estimated posterior median treatment differences (GSK2586881 – Placebo) and 95% credible intervals for the change from baseline at times T1 to T4 along with posterior probabilities of interest (for Part 1 and Part 2) Figure of absolute Oxygen Saturation by timepoint (for Part 1 and Part 2) Figure of statistical analysis adjusted change from baseline medians and 95% credible intervals by treatment group and timepoint (for Part 1 and Part 2)

Planned Statistical Analyses
Endpoint(s)

 Pulmonary Vascular Resistance (PVR)
Model Specification

 Refer to Section 7.2. PVR will be analysed in the same manner as for the primary endpoint PASP. Posterior probabilities of interest to include (looking for high probabilities to favour increases to a lesser extent in PVR on GSK2586881): 
 Probability that change from baseline in PVR is reduced by GSK2586881 (i.e., probability that a treatment difference is negative, or if a log transformation is applied then the probability that the ratio is less than 1). Probability that change from baseline in PVR is reduced by >=0.1 wood units and >=0.3 wood units (i.e., probability that a treatment difference is <=-0.1 wood units and <=-0.3 wood units. In the case of a log-transformation, ratios of interest would be <0.95 and 0.90, representing 5% and 10% difference between groups) Probability cut-offs may be re-assessed at the time of analysis
Model Checking

 Refer to: Appendix 8: Model Checking and Diagnostics for Statistical Analyses
Model Results Presentation (Part 2 only)

 Summary tables for absolute and change from baseline by treatment and timepoint (T0 to T4) Listing of absolute data Individual subject profiles by treatment group and timepoint

Planned Statistical Analyses

- Summary table of statistical analysis, adjusted change from baseline posterior medians and 95% credible intervals by treatment and timepoint, together with estimated posterior median treatment differences (GSK2586881 – Placebo) and 95% credible intervals for the change from baseline at times T1 to T4 along with posterior probabilities of interest
- Figure of absolute PVR by timepoint
- Figure of statistical analysis adjusted change from baseline medians and 95% credible intervals by treatment group and timepoint

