Analysis Populations	
 All Subjects Screened Population will contain all subjects that complete at least one Visit 1 (Screening) procedure. The Modified Intent-to-Treat (mITT) Population will comprise all randomised subjects, excluding those who were randomised in error. The Modified Intent-to-Treat (mITT1) Part 1 Population will comprise all subjects in the mITT Population, who were randomised into Part 1 of the study. The Modified Intent-to-Treat (mITT2) Part 2 Population will comprise all subjects in the mITT Population, who were randomised into Part 2 of the study The Pharmacokinetic (PK) Population will comprise all subjects in the mITT Population, for whom a PK sample was obtained and analysed and on active treatment.

Overview	Key Elements of the RAP
	
 The Pharmacokinetic (PK1) Population Part 1 will comprise all subjects in the mITT Population, randomised in Part 1 of the study, for whom a PK sample was obtained and analysed and on active treatment. The Pharmacokinetic (PK2) Population Part 2 will comprise all subjects in the mITT Population, randomised in Part 2 of the study, for whom a PK sample was obtained and analysed and on active treatment.
Hypothesis	
 No formal statistical hypotheses are being tested. A Bayesian statistical analysis framework with non-informative priors for model parameters (unless otherwise specified) will be used to obtain posterior distributions for effects of interest. These posterior distributions will be used to obtain a number of probability statements about the magnitude of treatment effects (e.g. probability of any treatment related reduction in PASP, or probability that the treatment related reduction in PASP ≥ 5 mmHg). A rule of thumb for “end of study success” is if the probability of any treatment related reduction in PASP (T3-T0) exceeds 0.95 (success is also conditional on the probability of (absolute) treatment related reductions in oxygen saturation exceeding 5% being small).
Primary Analyses	
 The primary endpoint, change from baseline in PASP following exercise under hypoxic conditions (Ti-T0) will be analysed using a Bayesian repeated measures mixed effects regression model, to compare the effects of Placebo vs GSK2586881. Analyses will be performed for Part 1 and Part 2 separately.

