7.2. Planned Statistical Analyses

Primary Statistical Analyses
Endpoint
• Pulmonary Artery Systolic Pressure (PASP)
Model Specification

 • The description below describes the current thinking of how to analyse this endpoint. The proposed model will be assessed, and if not appropriate alternative models could be used. Reasons for and a full description of alternative modeling methods used would be fully documented in the CPSR. • The data will be inspected prior to analysis to determine whether a data transformation is required. Any data transformations (e.g. natural logarithm) will be applied to observed individual data prior to any modeling or derivations (e.g. prior to deriving subject baseline) • Separate analyses will be performed for Part 1 and Part 2 of the study. • A Bayesian repeated measures mixed effects model (fitted using SAS PROC MCMC), will be used to model the change from baseline (Ti-T0) in PASP. Based on the study design there are 4 post-dose timepoints (T1, T2, T3 and T4). The timepoint of primary interest is T3; in Part 1 this is immediately after exercise at an altitude of 4000m and in Part 2, this is 2 minutes into a reduced exercise challenge at an altitude of 5000m. • Covariates for period, treatment and timepoint (i.e., T1 to T4) will be included as fixed effects. Adjusted period-specific baseline and subject-level baseline will be included as continuous parameters (see Section 10.3.2.1). Subject will be included as a random effect and timepoint will be included as a repeated effect. Treatment by timepoint and adjusted period-specific baseline by timepoint interactions will be included. An unstructured variance-covariance matrix

Primary Statistical Analyses

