3.10.	miTT2	PFT3	Summary of Oxygen Saturation Change from Baseline (Part 2)	As above (Part 2 population)	SAC (GSK)
3.11.	miTT1	SAFE_T1 (non-standard)	Summary of Repeated Measures Bayesian Statistical Analysis of Change from Baseline in Oxygen Saturation (Part 1)	As per SAFE_T1 but parameter column could be removed. Note that adjusted treatment differences are included on page 2 of mock example. For OS expecting that we'll need to update the Posterior Probability labels, to <0%, <-3%, <-5%, where 5% is the clinical concern level for a treatment difference where GSK reduces OS to a greater extent. Please see Section 8.1.2 with regards to changes required should a log transformation be needed (SAFE_T2 applies in this case with addition of posterior probabilities to be added).	IA[1], SAC (GSK)
3.12.	miTT2	SAFE_T1 (non-standard)	Summary of Repeated Measures Bayesian Statistical Analysis of Change from Baseline in Oxygen Saturation (Part 2)	As above (Part 2 population)	SAC (GSK)
Pulmonary Vascular Resistance (PVR)					
3.13.	miTT2	PFT1	Summary of Pulmonary Vascular Resistance (PVR) (Part 2)	See comments for PASP	SAC (GSK)
3.14.	miTT2	PFT3	Summary of Pulmonary Vascular Resistance Change from Baseline (PVR) (Part 2)	See comments for PASP	SAC (GSK)
3.15.	miTT2	SAFE_T1 (non-standard)	Summary of Repeated Measures Bayesian Statistical Analysis of Change from Baseline in Pulmonary Vascular Resistance (PVR) (Part 2)	See comments for PASP. Note that adjusted treatment differences and posterior probabilities would initially be (<0, <0.1, <0.3)	SAC (GSK)

Safety : Tables					
No.	Population	IDSL / TST ID / Example Shell	Title	Programming Notes	Deliverable [Priority]
Adverse Events (AEs)					
3.16.	mITT1	AE1CP (same as CP_AE1x)	Summary of All Adverse Events by System Organ Class and Preferred Term (Part 1)	Summarise by treatment group. Any pre-treatment AEs to be included in the listing only. Will only be created for interim if sufficient number of AEs are observed.	IA[1] (GSK), SAC (FSP)
3.17.	mITT2	AE1CP (same as CP_AE1x)	Summary of All Adverse Events by System Organ Class and Preferred Term (Part 2)	As above (Part 2 population)	SAC (FSP)
3.18.	mITT1	AE1CP (same as CP_AE1x)	Summary All Drug-Related Adverse Events by System Organ Class and Preferred Term (Part 1)	Summarise by treatment group.	SAC
3.19.	mITT2	AE1CP (same as CP_AE1x)	Summary All Drug-Related Adverse Events by System Organ Class and Preferred Term (Part 2)	As above (Part 2 population)	SAC

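### The ratio cut-offs planned for log-transformed oxygen saturation (0.94 and 0.92) are not the counterparts of the 3- and 5-point absolute cut-offs, and they disagree with each other

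*SAP*

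**What the plan says.** SAP Section 8.1.2 analyses oxygen saturation with the primary model and looks for very low values of, among others, this quantity: "Probability that the change from baseline in Oxygen Saturation is reduced by GSK by >3% and >=5% (absolute difference) compared to placebo". It spells this out as "probability that a treatment difference (absolute) is <-3% and <=-5" per cent. For a log-transformed analysis the cut-offs become "ratios of interest would be <0.94 and <0.92 representing 6% and 8% difference between groups". No reference saturation or derivation is given, and the section allows cut-offs to be re-assessed at analysis.

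Whether to transform is left open in Section 7.2: "The data will be inspected prior to analysis to determine whether a data transformation is required". Any transformation is applied to the individual values before change from baseline is derived.

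Two other places fix the role of the 5-point level. In the synopsis (Section 1, Hypothesis), end-of-study success is a rule of thumb on pulmonary artery systolic pressure (PASP), and "success is also conditional on the probability of (absolute) treatment related reductions in oxygen saturation exceeding 5% being small". In Section 10.11.5, the programming note for Table 3.11 adds "where 5% is the clinical concern level for a treatment difference where GSK reduces OS to a greater extent". The same note then says "Please see Section 8.1.2 with regards to changes required should a log transformation be needed".

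For pulmonary vascular resistance (PVR), Section 8.1.2 pairs absolute reductions of 0.1 and 0.3 Wood units with a log alternative: "ratios of interest would be <0.95 and 0.90, representing 5% and 10% difference between groups".

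**The concern.** The ratios stand in for the absolute cut-offs when the scale changes, so one would expect them to represent about the same falls. They do not, and the two pairs imply different saturation levels.

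The oxygen check is passed when the probability is low. A ratio that needs a larger fall than the stated concern level gives a lower probability and makes the check easier to pass. The success condition is written in absolute points, but the log branch specifies no probability on that scale. Whoever judges the condition would have only the ratio probabilities to hand, plus descriptive absolute summaries.

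**Working it through.** **Inputs.** Absolute cut-offs d = 3 and 5 points; ratio cut-offs r = 0.94 and 0.92 (Section 8.1.2). Placebo saturation S at the timepoint is not in the SAP. It is an assumption here, shown over a range.

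**The plan's own figures.** 1 − 0.94 = 6% and 1 − 0.92 = 8%. The printed percentages are correct for the printed ratios.

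**Link between the scales.** Logs are taken before change is derived. The back-transformed effect is therefore (T3/T0 on active) / (T3/T0 on placebo). With equal baselines this is active saturation divided by placebo saturation at T3. Hence:
- ratio r is a fall of S × (1 − r) points;
- a fall of d points is the ratio 1 − d/S;
- the two agree only at S = d / (1 − r).

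**Implied saturation.**
- First pair: 3 / 0.06 = 50%.
- Second pair: 5 / 0.08 = 62.5%.

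No single S satisfies both. For comparison, the PASP pairs in Section 7.2 do agree: 2.5 / 0.05 = 50 mmHg and 5 / 0.10 = 50 mmHg.

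**Falls represented by the ratios, and ratios that would match.**

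| Assumed S | 0.94 in points | 0.92 in points | Ratio matching 3 | Ratio matching 5 |
|---|---|---|---|---|
| 50% | 3.0 | 4.0 | 0.940 | 0.900 |
| 62.5% | 3.75 | 5.0 | 0.952 | 0.920 |
| 70% | 4.2 | 5.6 | 0.957 | 0.929 |
| 80% | 4.8 | 6.4 | 0.9625 | 0.9375 |
| 90% | 5.4 | 7.2 | 0.967 | 0.944 |

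The 0.94 cut-off is looser than 3 points at any S above 50%. The 0.92 cut-off is looser than 5 points above 62.5% and stricter below it.

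**Effect on the reported probability (illustration, assumed inputs).** Take a posterior median difference of −4 points with SD 1.5. On the absolute scale, P(difference ≤ −5) = Φ((−5 + 4)/1.5) = 0.25. On the log scale use mean ln((S − 4)/S) and SD 1.5/(S − 4):
- S = 70%: P(ratio < 0.92) = 0.14
- S = 80%: 0.05
- S = 90%: 0.015

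With the matching ratio 0.9375 at S = 80%, the log-scale probability is 0.25. The gap therefore comes from the cut-off and not from the transformation.

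**PVR.** 0.1 / 0.05 = 2 Wood units; 0.3 / 0.10 = 3 Wood units. These pairs are also mutually inconsistent.

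**The case against.** **The change is open and correctly labelled.** A reader might infer that a log transformation would silently relax the oxygen limit under an unchanged label. The SAP does not support that. It prints 6% and 8%, calls the values ratios of interest without claiming they equal 3 and 5 points, and tells the programmer to update the table. This stands, so the fault is a mismatched choice of cut-offs without a derivation.

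**The success condition itself is unchanged.** It stays worded in absolute terms, is a rule of thumb, and leaves the meaning of small undefined; Section 2.4 states that there are no formal hypotheses. This stands too. What remains is that the log branch plans no posterior probability with which to judge that condition.

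**The branch is conditional.** Transformation depends on data inspection. Section 8.3.2 calls it highly likely only for the biomarkers, and Table 3.11 is assigned the untransformed shell by default. This limits the severity. The freedom to re-assess cut-offs at analysis is a weaker defence: the study is sponsor-open, so a safety cut-off could be chosen with treatment results in view.

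**A large fall would still show.** Assume S = 80%, a posterior mean of −5.5 and SD 1.2. Then P(fall ≥ 5 points) = Φ(0.5/1.2) = 0.66 and P(ratio < 0.92) = Φ(−0.9/1.2) = 0.23, which is not very low. P(ratio < 0.94) = Φ(0.7/1.2) = 0.72, and credible intervals and absolute summaries are also planned. This stands for marked desaturation. The distortion matters more for intermediate effects, such as 0.25 against 0.05 above.

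**Direction.** The SAP gives no saturation, so that the 5-point cut-off is loosened rests on S being above 62.5%.

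**Conclusion.** The point holds as a non-equivalence. Ratios 0.94 and 0.92 match 3 and 5 points only at 50% and 62.5% saturation, and this internal disagreement needs no outside figure. The direction and size rest on the assumed placebo saturation and on equal baselines. Over 70% to 90%, the ratio standing in for 5 points needs 5.6 to 7.2 points, and the one standing in for 3 points needs 4.2 to 5.4. Above 62.5%, the probability reported for the concern level is too low.

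The consequence arises only under a log transformation. The absolute quantity named in the success condition would then have no planned posterior probability. The documents do not support the stronger inference that the success rule itself is altered, or that oxygen saturation must never be transformed.

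The PVR pairs are inconsistent too, but PVR is an exploratory endpoint. With no reference level given, neither a direction nor a decision consequence can be shown. Should-fix.

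**What to change.** In Section 8.1.2, replace the ratio cut-offs for oxygen saturation in one of two ways.

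1. **Preferred.** If a log model is used, convert each MCMC draw to an absolute difference: model-based placebo level at that timepoint × (ratio − 1). As the model is for change, define that level explicitly, for example a stated reference baseline × the draw's adjusted placebo ratio. Report P(< −3 points) and P(≤ −5 points), and state that the latter is used to judge the oxygen condition in the synopsis.
2. **Alternative.** State one reference saturation S, fixed before the transformed results are seen, and derive both ratios as 1 − d/S.

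Align the programming notes for Tables 3.11 and 3.12. The PVR pairs can be handled the same way with 0.1 and 0.3 Wood units. Both options keep the sponsor's own thresholds. The cost is SAP wording plus one post-processing step on draws that already exist; data collection and the model are unaffected.

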1. REPORTING & ANALYSIS PLAN SYNOPSIS

Overview	Key Elements of the RAP
Purpose	
 The purpose of this Reporting and Analysis Plan is to describe all planned analyses and outputs required for the Clinical Study Report (CSR) of study 204987. This amendment covers changes to the study following the interim analysis review of 11 participants.
Protocol	
 This RAP amendment is based on the protocol (Dated 23/SEP/2016, GSK Document No.: 2016N283626_00) and protocol amendments 1 & 2 & 3 (Dated:24/FEB/2017, GSK Document No. : 2016N283626_01 & 07/MAR/2017, GSK Document No. : 2016N283626_02 & 06/MAR/2018 GSK Document No. : 2016N283626_03) of study GSK2586881/204987
Study Design	
 The study will be a single centre, randomised, placebo-controlled and double blind (sponsor open). Subjects will be randomised to receive a single IV dose of GSK2586881 or saline in a crossover design. Approximately 25 subjects will be enrolled to ensure that a minimum of 20 subjects complete all dosing and critical assessments (the target of 20 may be revised by the sample size re-estimation)
Primary Objective	
 To evaluate the effect of a single IV dose of GSK2586881 on the HPV response in healthy volunteers during exercise under hypoxic conditions
Primary Endpoint	
 Change from baseline of Pulmonary Artery Systolic Pressure (PASP) measured via Echocardiography
Planned Analyses	
 An Interim Analysis was planned after approximately 10 patients had completed periods 1 and 2 of the study, to aid the team in decision making with regards to stopping the study for futility or a re-assessment of sample size. Following the interim (referred to as study Part 1), amendments were made to the study before re-starting Part 2. Further interim reviews are planned when approximately 3 and 6 participants have completed periods 1 and 2 in Part 2 of the study. All decisions regarding final analysis, as defined in this RAP document, will be made prior to Database Freeze.

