3.2. Final Analyses

The final planned primary analyses will be performed after the completion of the following sequential steps:

1. All subjects have completed the study as defined in the protocol (and subject to decisions made from the interim analyses).
2. All required database cleaning activities have been completed and final database release and database freeze has been declared by Data Management.
3. All criteria for unblinding the randomisation codes have been met (note that the study is being run as sponsor-unblinded, however, only a partial randomisation schedule will be made available to the GSK programming team for the interim analysis).
4. Randomisation codes have been distributed according to RandAll NG procedures.

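### Cut-offs for the posterior probabilities may be re-assessed at analysis, after freeze and code release, although the synopsis puts all final-analysis decisions before freeze

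*SAP*

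**What the plan says.** Sections 7.2 (PASP), 8.1.2 (oxygen saturation, and again PVR) and 8.3.2 (RAS peptides and surfactant protein D) each name thresholds for the treatment difference or ratio at which a posterior probability will be, or may be, reported. On the untransformed scale, the non-zero thresholds are reductions of 2.5 and 5 mmHg for PASP, 3 and 5 percentage points for saturation, and 0.1 and 0.3 Wood units for PVR. Each list closes with the same sentence: "Probability cut-offs may be re-assessed at the time of analysis".

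The synopsis, under Planned Analyses, states: "All decisions regarding final analysis, as defined in this RAP document, will be made prior to Database Freeze". Section 3.2 lists sequential steps that must be complete before the final primary analyses. One is that "final database release and database freeze has been declared by Data Management". Later steps are that the unblinding criteria are met and the codes distributed. The same section adds: "note that the study is being run as sponsor-unblinded".

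The synopsis, under Hypothesis, gives a rule of thumb for end-of-study success. It is met "if the probability of any treatment related reduction in PASP (T3-T0) exceeds 0.95", with the proviso that "success is also conditional on the probability of (absolute) treatment related reductions in oxygen saturation exceeding 5% being small". Section 2.4 says that there are no formal hypotheses and that the study is exploratory.

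**The concern.** Where nothing is formally tested, the posterior probabilities at named thresholds are a main part of the inferential output. Their value as advance statements depends on the thresholds being settled before anyone has seen which threshold suits the data. The SAP grants an explicit permission to revisit them, four times. It gives no trigger, no deadline, no blinding condition and no duty to keep reporting the listed values.

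The saturation threshold matters most. The 5% is more than a display choice, because the rule of thumb for success refers to it and the programming note for Table 3.11 calls it the level of clinical concern. A threshold changed once the posterior is known would be data-driven, even if changed in good faith.

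**Working it through.** **Timing, set side by side**

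1. Synopsis, Planned Analyses: decisions on the final analysis come before Database Freeze.
2. Section 3.2: the final analysis comes after freeze, after the unblinding criteria are met and after code distribution.
3. Sections 7.2, 8.1.2 (twice) and 8.3.2: cut-offs may be revisited at the time of analysis.

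By (2), the moment named in (3) falls after the deadline in (1). Choosing a reporting threshold is a decision about the final analysis. The statements therefore conflict on their face.

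**Part 1 results.** Section 3.1.1 records that the interim analysis was done, with 10 subjects analysed for the primary endpoint. Its planned output for PASP and saturation included posterior probabilities from the models of Sections 7.2 and 8.1.2. Tables 3.5 and 3.11 (Part 1) are marked for both that interim and the final analysis. A change to a Part 1 cut-off at final analysis would thus follow a planned sponsor review of Part 1 posterior probabilities.

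**Contrast within the SAP.** Section 7.2 requires the reasons for any alternative model to be documented in the study report. Appendix 11 ties a possible switch of biomarker analyses from Part 2 to Part 1 to a discussion at database freeze. The cut-off clause has neither safeguard.

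**How much the choice matters (illustration only).** The SAP states no SD, so there is no figure of its own to reproduce.

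- From the SAP: n = 14, the maximum to be randomised in Part 2 (Section 3.1.2); cut-offs c = -3 and -5 points (Section 8.1.2).
- Assumed: posterior approximately normal under the flat priors; estimate m = -3 points; SD of the within-subject difference 3, 5 or 7 points.
- Formula: P(difference < c) = Φ((c − m) / (SD/√n)).

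| SD | SD/√14 | P beyond 3 points | z at -5 | P beyond 5 points |
|---|---|---|---|---|
| 3 | 0.802 | 0.50 | -2.49 | 0.006 |
| 5 | 1.336 | 0.50 | -1.50 | 0.067 |
| 7 | 1.871 | 0.50 | -1.07 | 0.143 |

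With n = 10, as analysed in Part 1, and the same estimate, the last column becomes 0.018, 0.103 and 0.183. With n = 14 and an estimate of -4, the probabilities beyond 3 points are 0.894, 0.773 and 0.704, and those beyond 5 points are 0.106, 0.227 and 0.296.

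Only the SAP's own two cut-offs are used. The same data give very different reported probabilities depending on which one is shown.

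**The case against.** The strongest reply is that little hangs on this. Success is a rule of thumb in an exploratory study without formal hypotheses, so there is no error rate to inflate. That stands.

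A reader might infer that the whole success criterion can be moved after the results are seen. The SAP does not support that. The clause follows lists of effect sizes, so it most naturally concerns those. The PASP limb uses a threshold of zero and a probability of 0.95, and the 0.95 appears in the synopsis, not in Section 7.2. The 5% saturation value is also written into the synopsis, where no re-assessment clause is attached. But Section 8.1.2 lists the same 5% among the values it leaves open. The fair statement is that its status is ambiguous, not that it is movable.

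A reader might also infer that a changed cut-off could not be detected. It could: the listed values are in the SAP, and posterior medians with 95% credible intervals are reported in any case, so a probability at another threshold can be approximated. Nor were the biomarker cut-offs fixed and then reopened, since Section 8.3.2 offers them only as values that may be included.

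Sponsor access has limits too. Section 3.2 gives the programming team only a partial randomisation schedule for the interim, and Section 3.1.1 restricts Part 1 interim results to selected team members. Finally, the text permits changes after results are known but states no intention to make them.

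None of this reconciles the timing of the clause with the synopsis.

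**Conclusion.** The contradiction is real, and it rests on the wording alone: four clauses allow at analysis what the synopsis says is settled before freeze. The consequence is a weakness of pre-specification for the effect-size cut-offs, together with an unclear status for the 5% saturation value.

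The numerical size depends on assumed SDs and an assumed estimate. At n = 14 and an estimate of -3 points, the reported probability is 0.50 at the 3-point cut-off and about 0.006 to 0.14 at the 5-point one. This shows that the choice affects what is reported. It does not show that a success conclusion would reverse, because the SAP puts no number on a small probability. That omission is a separate matter and does not carry this point.

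**What to change.** Replace the clause in Sections 7.2, 8.1.2 (both endpoints) and 8.3.2 with wording to this effect:

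- cut-offs may be re-assessed only before Database Freeze, with the change and its reason documented;
- the PASP, saturation and PVR cut-offs listed in the SAP are always reported;
- any cut-off added later is shown beside them and labelled post hoc.

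In the synopsis, state that the 5% in the success rule is not subject to re-assessment at analysis, so that it agrees with Section 8.1.2.

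The cost is SAP wording only. Data collection, model and sample size are unchanged, and the sponsor can still add labelled post hoc probabilities.
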